### 2.2.1. Primary Estimand(s)

The co-primary estimands of this study are using composite estimands. The estimands are defined according to the co-primary objectives and are in alignment with the co-primary endpoints. It includes the following 4+1 attributes:

- Treatment: Zavegepant and placebo;
- Population: All randomized participants with migraine headache of moderate or severe intensity who took study intervention;
- Variable: Percentage of participants with pain intensity of none (pain freedom) at 2 hours postdose and separately, the percentage of participants with an MBS reported on study before dosing that is absent at 2 hours postdose. The MBS before dosing is reported as nausea, phonophobia, or photophobia. Symptom status is reported postdose as present or absent for each symptom (nausea, phonophobia, photophobia);

- Intercurrent event(s): Taking rescue medication at or before 2 hours postdose will be regarded as a failure.
- Population-level summary: Difference in percentages between zavegepant and placebo groups.

### 2.2.2. Secondary Estimand(s)

The secondary efficacy estimands of this study are using composite estimands. The estimands are defined according to the secondary efficacy objectives and are in alignment with the following secondary endpoints. It includes the following 4+1 attributes:

- Treatment: Zavegepant and placebo;
- Population: All randomized participants with migraine headache of moderate or severe intensity who took study intervention;
  - For the objective of evaluating return to normal function, phonophobia freedom, photophobia freedom, and nausea freedom at 2 hours postdose, the population will be participants defined above who had functional disability (mildly impaired, severely impaired, or requires bedrest), phonophobia presence, photophobia presence, and nausea presence, respectively, at the time of dosing.
  - For the objective of evaluating pain relapse, the population will be participants defined above who had pain freedom at 2 hours postdose.
- Variable:
  - Percentage of participants with a pain intensity of none or mild (pain relief) at 15 minutes, 30 minutes, 60 minutes, 2 hours postdose, at all time points from 2 to 24 hours postdose, at all time points from 2 to 48 hours postdose, respectively.
  - Percentage of participants with a functional disability level of normal at 15 minutes, 30 minutes, 60 minutes and 2 hours postdose, respectively.
  - Percentage of participants with phonophobia absence, with photophobia absence, with nausea absence at 2 hours postdose, respectively.
  - Percentage of participants with a pain intensity of none (pain freedom) at all time points from 2 to 24 hours postdose, at all time points from 2 to 48 hours postdose, respectively.
  - Percentage of participants with a pain intensity of mild, moderate, or severe (pain relapse) at any time point after 2 hours postdose.

- Intercurrent event(s): Taking rescue medication at or before the corresponding assessed time points as specified in the endpoints postdose will be regarded as a failure.
- Population-level summary: Difference in percentage of participants achieving the specific outcome at time points of interest between zavegepant and placebo groups.

The secondary efficacy estimand for objective of rescue medication use is defined by the following attributes:

- Treatment: Zavegepant and placebo;
- Population: All randomized participants with migraine headache of moderate or severe intensity who took study intervention;
- Variable: Percentage of participants taking rescue medication within 24 hours postdose;
- Intercurrent event(s): No relevant intercurrent event is considered since taking rescue medication is the analysis objective.
- Population-level summary: Difference in percentages between zavegepant and placebo groups.

### **2.2.3. Tertiary/Exploratory Estimand(s)**

The exploratory estimand is a composite estimand. The estimand is defined according to the exploratory objectives and is in alignment with the following exploratory endpoints. It includes the following 4+1 attributes:

- Treatment: Zavegepant and placebo;
- Population: All randomized participants with migraine headache of moderate or severe intensity who took study intervention;
  - For the objective of evaluating return to normal function, phonophobia freedom, photophobia freedom, and nausea freedom at the specified time point postdose, the population will be participants defined above who had functional disability (mildly impaired, severely impaired, or requires bedrest), phonophobia presence, photophobia presence, and nausea presence, respectively, at the time of dosing.
- Variable:
  - Percentage of participants with a pain intensity of none (pain freedom) at 15 minutes, 30 minutes, 45 minutes, 60 minutes, 90 minutes, 2 hours, 3 hours, 4 hours, 6 hours, 8 hours, 24 hours, and 48 hours postdose, respectively.

- Percentage of participants with an MBS reported before dosing that is absent at 15 minutes, 30 minutes, 45 minutes, 60 minutes, 90 minutes, 2 hours, 3 hours, 4 hours, 6 hours, 8 hours, 24 hours, and 48 hours postdose, respectively.
- Percentage of participants with a pain intensity of none or mild (pain relief) at 15 minutes, 30 minutes, 45 minutes, 60 minutes, 90 minutes, 2 hours, 3 hours, 4 hours, 6 hours, 8 hours, 24 hours, and 48 hours postdose, respectively.
- Percentage of participants with a functional disability level of normal at 15 minutes, 30 minutes, 45 minutes, 60 minutes, 90 minutes, 2 hours, 3 hours, 4 hours, 6 hours, 8 hours, 24 hours, and 48 hours postdose, respectively.
- Percentage of participants with phonophobia absent at 15 minutes, 30 minutes, 45 minutes, 60 minutes, 90 minutes, 2 hours, 3 hours, 4 hours, 6 hours, 8 hours, 24 hours, and 48 hours postdose, respectively.
- Percentage of participants with photophobia absent at 15 minutes, 30 minutes, 45 minutes, 60 minutes, 90 minutes, 2 hours, 3 hours, 4 hours, 6 hours, 8 hours, 24 hours, and 48 hours postdose, respectively.
- Percentage of participants with nausea absent at 15 minutes, 30 minutes, 45 minutes, 60 minutes, 90 minutes, 2 hours, 3 hours, 4 hours, 6 hours, 8 hours, 24 hours, and 48 hours postdose, respectively.
- Intercurrent event(s): Taking rescue medication at or before the corresponding assessed time points as specified in the endpoints postdose will be regarded as a failure.
- Population-level summary: Difference in percentage of participants achieving the specific outcome at time points of interest between zavegepant and placebo groups.

### 2.3. Study Design

This is a Phase 3, randomized, double-blind, placebo-controlled, multicenter, single-attack, outpatient evaluation of the efficacy and safety of zavegepant versus placebo for the acute treatment of migraine in Asian adults. The study intervention is formulated as zavegepant 10 mg IN or matching placebo. The study intervention will be administered using an unidose nasal spray device containing a single dose of zavegepant or matching placebo. The participants will be instructed to take their study intervention, as an outpatient, if they have a migraine headache which reaches moderate or severe pain intensity.

The total duration of study participation will be up to approximately 16 weeks. This includes a 3-28 day Screening Phase, a Treatment Phase that can last up to 45 days or until the participant has a migraine headache that reaches moderate or severe pain intensity, followed by an EOT Visit 7 (+2) days after the administration of study intervention and a Follow-Up Visit 28-35 days after the administration of study intervention for safety monitoring.

Approximately 1750 participants will be screened to randomize approximately 1400 participants in a 1:1 ratio between the 2 treatment groups (zavegepant or placebo). Before any study procedures are performed, participants must sign informed consent. After informed consent is signed, participants will be enrolled in the IRT system. The participant's migraine history and medical history will be collected at the Screening Visit. Participants will also undergo all screening procedures as indicated in the SoA. Screening Visit must be completed in person.

Within 3-28 days from the Screening Visit, participants will return to the site for the Baseline (Randomization) Visit. Participants who meet all eligibility criteria may be randomized at the Baseline Visit. After randomization is completed in the IRT, study intervention will be dispensed to participants to take home for a single attack of moderate or severe pain intensity occurring up to 45 days after the Baseline (Randomization) Visit. The participants will be provided with an eCOA handheld device. The eCOA handheld device may also be referred to as a handheld or an eDiary. Once a participant experiences a migraine headache of moderate to severe intensity, they should record this in the handheld. The handheld will instruct the participant to take study intervention after the initial assessments are completed in the device. The participant will complete assessments for 48 hours after taking study intervention to record efficacy and other quality of life measures. The study personnel **MUST** instruct and train the participant on the proper use of the handheld to **ENSURE** proper understanding and use of the tool, **PRIOR** to the participant leaving the office at Baseline Visit. Baseline Visit must be completed in person. **Participants in this study may be randomized only once. Under NO circumstances may a participant be re-randomized.**

Participants should be encouraged to treat their **FIRST** qualifying migraine attack (moderate or severe pain intensity) that occurs during the Treatment Phase. If participants are unable to treat their first qualifying migraine, refer to Protocol Section 6.9.2. Rescue Medication for a list of medications that are allowed during the course of this study.

[figure not shown]
Participants will return to the site for EOT Visit (after assessments in the handheld are completed) within 7 (+2) days after administration of study intervention. The "+2" day window is included for scheduling purposes only. Every effort should be made to conduct the EOT Visit within the specified window of 7 (+2) days after administration of study intervention. At the EOT Visit, medication compliance and monitoring of safety assessments will be performed as indicated in the SoA. If a participant has **NOT** treated a migraine attack with study intervention within 45 days after randomization, they are still required to complete all EOT Visit procedures. All participants must return used and unused study intervention and their handheld device to site. Certain provisions may be implemented, in order to minimize potential hazards to the participants due to COVID-19 **ONLY** at the EOT Visit. These provisions may allow alternatives to in-person study visits and include but are not limited to the following: conducting remote study visits via phone/telemedicine video, focusing on safety assessments during remote visits, performing safety labs via local labs or professional in-home phlebotomy vendors, and shipping of study intervention if needed. Any potential issues should be discussed with sponsor and will be addressed on an individualized basis. Components of the EOT Visit may be conducted under the provisions mentioned above (remote via phone/telemedicine, local labs, etc.), and the window visit may be

extended by 5 days due to COVID-19 **ONLY** if circumstances warrant in order to minimize any potential risks to participant safety.

Follow-Up Visit will occur 28-35 days after treatment for safety follow-up of AEs and/or abnormal laboratory tests. Participants may be contacted via telephone. Every effort should be made to conduct the Follow-Up Visit within 28-35 days after treatment. If a participant has NOT treated a migraine attack with study intervention within 45 days after randomization, they are not required to complete the Follow-Up Visit.

090177e1a3a7d3d9\Approved\Approved On: 30-May-2025 05:10 (GMT)

Figure 1. Study Design

### 3. ENDPOINTS AND BASELINE VARIABLES: DEFINITIONS AND CONVENTIONS

#### 3.1. Primary Endpoint(s)

The co-primary endpoints are the percentage of participants with a pain intensity of none (pain freedom) at 2 hours postdose, and separately, the percentage of participants with an MBS reported before dosing that is absent at 2 hours postdose.

#### 3.2. Secondary Endpoint(s)

##### 3.2.1. Key Secondary Endpoints

- Percentage of participants with a pain intensity of none or mild (pain relief) at 15 minutes postdose.
- Percentage of participants with a pain intensity of none or mild (pain relief) at 30 minutes postdose.
- Percentage of participants with a pain intensity of none or mild (pain relief) at 2 hours postdose.
- Percentage of participants with a functional disability level of normal at 2 hours postdose, evaluated for participants with functional disability at the time of dosing.
- Percentage of participants with a pain intensity of none or mild at all time points from 2 to 24 hours postdose (sustained pain relief).
- Percentage of participants with a pain intensity of none or mild at all time points from 2 to 48 hours postdose (sustained pain relief).
- Percentage of participants with a functional disability level of normal at 30 minutes postdose, evaluated for participants with functional disability at the time of dosing.
- Percentage of participants with a functional disability level of normal at 60 minutes postdose, evaluated for participants with functional disability at the time of dosing.

##### 3.2.2. Other Secondary Endpoints

- Percentage of participants with phonophobia absent at 2 hours postdose, evaluated for participants with phonophobia present at the time of dosing.
- Percentage of participants with photophobia absent at 2 hours postdose, evaluated for participants with photophobia present at the time of dosing.
- Percentage of participants with nausea absent at 2 hours postdose, evaluated for participants with nausea present at the time of dosing.

- Percentage of participants with a pain intensity of none at all time points from 2 to 24 hours postdose (sustained pain freedom).
- Percentage of participants with a pain intensity of none at all time points from 2 to 48 hours postdose (sustained pain freedom).
- Percentage of participants with pain relapse (any pain intensity above ‘none’) at any time point after 2 hours postdose, evaluated for participant with pain freedom at 2 hours postdose.
- Percentage of participants taking rescue medication within 24 hours postdose.
- Percentage of participants with a pain intensity of none or mild (pain relief) at 60 minutes postdose.
- Percentage of participants with a functional disability level of normal at 15 minutes postdose, evaluated for participants with functional disability at the time of dosing.
- Number and percentage of participants with AEs of moderate or severe intensity, SAEs, local irritation AEs, and grade 3 or 4 laboratory test abnormalities.

### 3.3. Other Endpoint(s)

The exploratory endpoints include:

- Percentage of participants with a pain intensity of none (pain freedom) at 15 minutes, 30 minutes, 45 minutes, 60 minutes, 90 minutes, 2 hours, 3 hours, 4 hours, 6 hours, 8 hours, 24 hours, and 48 hours postdose, respectively.
- Percentage of participants with an MBS reported before dosing that is absent at 15 minutes, 30 minutes, 45 minutes, 60 minutes, 90 minutes, 2 hours, 3 hours, 4 hours, 6 hours, 8 hours, 24 hours, and 48 hours postdose, respectively.
- Percentage of participants with a pain intensity of none or mild (pain relief) at 15 minutes, 30 minutes, 45 minutes, 60 minutes, 90 minutes, 2 hours, 3 hours, 4 hours, 6 hours, 8 hours, 24 hours, and 48 hours postdose, respectively.
- Percentage of participants with a functional disability level of normal at 15 minutes, 30 minutes, 45 minutes, 60 minutes, 90 minutes, 2 hours, 3 hours, 4 hours, 6 hours, 8 hours, 24 hours, and 48 hours postdose, respectively.
- Percentage of participants with phonophobia absent at 15 minutes, 30 minutes, 45 minutes, 60 minutes, 90 minutes, 2 hours, 3 hours, 4 hours, 6 hours, 8 hours, 24 hours, and 48 hours postdose, respectively.

- Percentage of participants with photophobia absent at 15 minutes, 30 minutes, 45 minutes, 60 minutes, 90 minutes, 2 hours, 3 hours, 4 hours, 6 hours, 8 hours, 24 hours, and 48 hours postdose, respectively.
- Percentage of participants with nausea absent at 15 minutes, 30 minutes, 45 minutes, 60 minutes, 90 minutes, 2 hours, 3 hours, 4 hours, 6 hours, 8 hours, 24 hours, and 48 hours postdose, respectively.
- Percentage of participants with the overall status improvement at 30 minutes, 60 minutes, 2 hours, and 24 hours postdose, and the total score of PGIC.

### 3.4. Baseline Variables

The Baseline variables in the study contain demographic and other baseline characteristics as follows.

- Age in years at informed consent (years)
- Age at informed consent category 1:  $<40, \geq 40$
- Age at informed consent category 2:  $<65, \geq 65$
- Sex: male, female
- Height (cm)
- Weight (kg)
- BMI ( $\text{kg}/\text{m}^2$ )
- BMI category:  $<25 \text{ kg}/\text{m}^2, \geq 25 \text{ to } <30 \text{ kg}/\text{m}^2, \geq 30 \text{ kg}/\text{m}^2$
- Race
- Country/region at randomization
- Stable prophylactic migraine medication use through randomization: yes, no.

### 3.5. Safety Endpoints

#### 3.5.1. Adverse Events

SAEs and non-serious AEs should be reported from signing of consent through and including a minimum of 28 calendar days after the last administration of the study intervention. The following other significant AEs will be assessed: hepatic-related AEs, potential drug abuse AEs, cardiovascular AEs, suicidality AEs, local irritation AEs, hypertension AEs, and Raynaud's phenomenon AEs.

#### 3.5.2. Laboratory Data

Clinical safety laboratory testing will be performed at Screening, EOT/Early Discontinuation Visits. The baseline value is defined as the last non-missing value on or before the study intervention start date/time.

### 3.5.3. Vital Signs

The vital signs will be measured at Screening, Baseline, EOT/Early Discontinuation Visits. Vital signs include systolic blood pressure, diastolic blood pressure and pulse rate. The baseline value is defined as the last non-missing value on or before the study intervention start date/time.

### 3.5.4. 12-lead Electrocardiograms

A 12-lead ECG will be measured at Screening, EOT/Early Discontinuation Visits. ECG parameters include QRS, PR, QT, QTcF, and heart rate. The baseline value is defined as the last non-missing value on or before the study intervention start date/time.

### 3.5.5. Columbia Suicide Severity Rating Scale (C-SSRS)

The Columbia-Suicide Severity Rating Scale (C-SSRS) is a questionnaire used for suicide assessment. The C-SSRS will be assessed at Screening, Baseline, EOT/Early Discontinuation Visits.

The C-SSRS is made up of ten categories, all of which maintain binary responses (yes/no) to indicate a presence or absence of the suicidal thought or behavior. The C-SSRS findings will be recorded as AEs.

## 4. ANALYSIS SETS (POPULATIONS FOR ANALYSIS)

Data for all participants will be assessed to determine if participants meet the criteria for inclusion in each analysis population prior to unblinding and releasing the database and classifications will be documented per standard operating procedures.

Population	Description	Applicable Analysis (for additional information refer to section 6)
Enrolled	"Enrolled" means a participant's, or their legally authorized representative's, agreement to participate in a clinical study following completion of the informed consent process and assignment to study intervention. A participant will be considered enrolled if the informed consent is not withdrawn prior to participating in any study activity after screening. Potential participants who are screened for the purpose of determining eligibility for the study, but do not participate in the study, are not considered enrolled, unless otherwise specified by the protocol.	Baseline and other summaries (Section 6.5.2 and Section 6.5.3)

Population	Description	Applicable Analysis (for additional information refer to section 6)
FAS	All participants in the enrolled analysis set who are randomly assigned to study intervention (zavegepant or placebo).	Baseline and other summaries (Section 6.5.2 and 6.5.4)
EAS	All participants in the full analysis set who satisfy the following criteria: 
 
• Randomized only once
 
• Have a migraine of moderate or severe pain intensity at the time of dosing
 
• Take study intervention (zavegepant or placebo)
 
• Have postdose efficacy data (ie, non-missing pain intensity, phonophobia status, photophobia status, nausea status, or functional disability level with finding date/time after the study intervention start date/time).
 
	Primary endpoints, secondary endpoints, exploratory endpoints, and baseline summaries (Sections 6.1, 6.2, 6.3, and 6.5.1)
Safety analysis set	All participants in the enrolled analysis set who take study intervention (zavegepant or placebo).	Baseline and other summaries (Section 6.5); Safety summaries and analyses (Section 6.6)

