### **9.1.1. Estimands**

#### **9.1.1.1. Primary Estimand/Co-primary Estimands**

The co-primary estimands are defined by the following attributes:

- Population: all randomized participants with migraine headache of moderate or severe intensity who took study intervention.
- Endpoints: percentage of participants with pain intensity of none at 2 hours postdose and separately, the percentage of participants with an MBS reported on study before dosing that is absent at 2 hours postdose. The MBS before dosing is reported as nausea, phonophobia, or photophobia. Symptom status is reported postdose as present or absent for each symptom (nausea, phonophobia, and photophobia).
- Treatment condition: zavegepant and placebo.
- Intercurrent event: taking rescue medication at or before 2 hours postdose will be regarded as a failure.
- Population-level summary: difference in percentages between treatment groups.

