## 9.2. Analysis Sets

For purposes of analysis, the following analysis sets are defined:

Participant Analysis Set	Description
Enrolled	"Enrolled" means a participant's, or their legally authorized representative's, agreement to participate in a clinical study following completion of the informed consent process and assignment to study intervention. A participant will be considered enrolled if the informed consent is not withdrawn prior to participating in any study activity after screening. Potential participants who are screened for the purpose of determining eligibility for the study, but do not participate in the study, are not considered enrolled, unless otherwise specified by the protocol.
FAS	All participants in the enrolled analysis set who are randomly assigned to study intervention (zavegepant or placebo).
EAS	All participants in the full analysis set who satisfy the following criteria: 
 
• Randomized only once
 
• Have a migraine of moderate or severe pain intensity at the time of dosing
 
• Take study intervention (zavegepant or placebo)
 
• Have postdose efficacy data (ie, non-missing pain intensity, phonophobia status, photophobia status, nausea status, or functional disability level with
 

Participant Analysis Set	Description
	finding date/time after the study intervention date/time).
Safety analysis set	All participants in the enrolled analysis set who take study intervention (zavegepant or placebo).

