#### 9.3.2. Primary Endpoint(s)/Estimand(s) Analysis

##### 9.3.2.1. Main Analytical Approach

Zavegepant will be tested for superiority against placebo at an  $\alpha=0.05$  level for both co-primary endpoints using the EAS. For each endpoint, treatment groups will be compared using a CMH test for the difference in percentages of participants achieving the endpoint response criteria (zavegepant-placebo) stratified by country/region. The stratified difference in percentages between treatment groups will be presented with p-value and a 95% CI based on normal approximation. For individual treatment group, the percentage of participants achieving the endpoint response criteria will be presented with a 95% CI based on normal approximation.

Participants with missing data at 2 hours postdose or taking rescue medication at or before 2 hours postdose will be classified as failures.

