### 5.3. Methods to Manage Missing Data

Missing data in analyses of binary endpoints are defined as follows:

- Non-Completer=Failure (NC=F): Participants with missing data at a single point are classified as failures. This missing data imputation method is applied to endpoints based on data from a single time point (e.g., co-primary endpoints) as the main analysis method.

- Non-Completer with missing data at more than 1 Time Point=Failure (NC1=F): Participants with missing data at >1 time point postdose in a specified time period are classified as failures. This missing data imputation method is applied to endpoints that are based on data from multiple time points (e.g., secondary endpoints of sustained pain freedom from 2 to 24 hours postdose) as the main analysis method.

In the sensitivity analysis of the co-primary endpoints, the following imputation strategies for missing data will be implemented.

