### Appendix 2.1.2. Rescue Medication = Failure (RM=F) Algorithm

Efficacy assessments that are affected by the RM=F algorithm are pain intensity, nausea status, photophobia status, phonophobia status, and functional disability level.

Let X denote a postdose time point: 15, 30, 45, 60, or 90 minutes; 2, 3, 4, 6, 8, 24, or 48 hours.

If study intervention start date/time is from the eDiary Migraine Report, then it can be linked with its corresponding data at postdose time point X.

For a given assessment at time point X, the objective is to determine whether any rescue medication is taken at or before that assessment, even if the assessment is missing.

Rescue medication taken at or before time point X (RM=F) is defined as either (1) or (2):

- 1) Rescue medication taken at or before the assessment in the X analysis window. Defined as either of the following if the assessment is non-missing in the X analysis window:
  - (first rescue medication date/time  $\leq$  {eDiary finding date/time for the assessment in the X analysis window}, if first rescue medication time is not missing

- (first rescue medication date  $\leq$  {eDiary finding date for the assessment in the X analysis window}, if first rescue medication date is not missing but time is missing
- 2) Rescue medication taken at or before the missing assessment in the X analysis window. Defined as either of the following if the assessment is missing in the X analysis window:
  - (first rescue medication date/time – study intervention start date/time)  $\leq$  upper bound of the X analysis window (see [Table 2](#)), if first rescue medication time is not missing
  - first rescue medication date  $\leq$  study intervention start date + Y days, if first rescue medication date is not missing but time is missing
    - If X < 24 hours, then Y = 0.
    - If X = 24 hours, then Y = 1.
    - If X = 48 hours, then Y = 2.

090177e1a3a7d3d9\Approved\Approved On: 30-May-2025 05:10 (GMT)

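### The efficacy analysis set drops treated participants who have no postdose entry at all, so the co-primary analyses cover a narrower group than the stated estimand

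*SAP*

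**What the plan says.** **Estimand.** Protocol 9.1.1.1 gives "Population: all randomized participants with migraine headache of moderate or severe intensity who took study intervention". SAP 2.2.1 has the same population. Neither requires any postdose data.

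**Analysis set.** Protocol 9.2 and SAP 4 define the EAS by four criteria. Three match the estimand or are administrative: randomized once, moderate or severe pain at dosing, study intervention taken. The fourth is "Have postdose efficacy data (ie, non-missing pain intensity, phonophobia status, photophobia status, nausea status, or functional disability level", recorded after dosing.

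**Where it is used.** Protocol 9.3.2.1 and SAP 6.1.1.1 and 6.1.2.1 run both co-primary analyses on the EAS. SAP Appendix 1 lists the EAS for the multiple-imputation and varying-response-rate sensitivity analyses too. The secondary and exploratory efficacy analyses use the EAS or subsets of it.

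**Failure rules.** Protocol 9.3.2.1: "Participants with missing data at 2 hours postdose or taking rescue medication at or before 2 hours postdose will be classified as failures". SAP 5.3 (NC=F): "Participants with missing data at a single point are classified as failures". For rescue medication (RM=F), SAP Appendix 2.1.2 states that "the objective is to determine whether any rescue medication is taken at or before that assessment, even if the assessment is missing". Protocol 6.9.2 and 8.2.3 have rescue use recorded on paper, separately from the handheld.

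**Declared changes.** SAP 2.1 lists none.

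**The concern.** Inclusion in the EAS depends partly on something that happens after randomization. Two treated participants can both lack a 2-hour value and be handled in opposite ways. One makes a single entry at 15 minutes and stops, and counts as a failure. The other makes no entry and leaves both numerator and denominator.

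The rescue case is sharper. Suppose a participant doses, takes rescue medication within 2 hours, writes it on the paper diary and never touches the handheld. The estimand calls that person a failure, and RM=F is built to work without an assessment, but the EAS removes the person before the rule applies.

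If the share with no entries differs between arms, the estimated difference moves away from the estimand. Both co-primaries must succeed before any key secondary endpoint is tested, so a borderline result on either one carries the whole hierarchy. The planned sensitivity analyses cannot reveal the problem, because they start from the same set.

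**Working it through.** **Inputs (Protocol 9.5).** 700 randomized per arm, of whom 90% are expected to have a headache: 700 × 0.90 = 630 per arm. Pain freedom 23.2% vs 15.1%. MBS freedom 40.5% vs 32.1%. Two-sided alpha 0.05.

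**Step 1: reproduce the stated power.** Unpooled normal approximation, no stratification: power = Φ(Δ/SE − 1.96), SE = √[p1(1−p1)/n1 + p2(1−p2)/n2].

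- Pain: 0.081/0.02205 = 3.673, power 95.7% (stated 95.7%).
- MBS: 0.084/0.02699 = 3.112, power 87.5% (stated 87.5%).
- Joint, as a product: 0.957 × 0.875 = 83.7% (stated about 84%).

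**Step 2: the estimand when no-entry participants are failures.** Let f be the share of treated participants with no postdose entry. If the planned rate p holds in the EAS, the rate among all treated is p(1 − f). The documents give no value for f, so every f below is an assumption. Each scenario has 630 *treated* per arm; the EAS then has 630(1 − f).

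| f, zavegepant / placebo | Pain, EAS | Pain, all treated | MBS, EAS | MBS, all treated |
|---|---|---|---|---|
| 1% / 1% | 8.10 | 8.02 | 8.40 | 8.32 |
| 5% / 5% | 8.10 | 7.70 | 8.40 | 7.98 |
| 3% / 1% | 8.10 | 7.56 | 8.40 | 7.51 |
| 1% / 3% | 8.10 | 8.32 | 8.40 | 8.96 |

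Differences are in percentage points. Example, MBS at 3%/1%: 40.5 × 0.97 − 32.1 × 0.99 = 39.285 − 31.779 = 7.51.

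**Step 3: MBS power on a like-for-like base of 630 treated per arm.**

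- 3%/1%, with exclusion (EAS of 611.1 and 623.7): 0.084/0.02727 = 3.080, power 86.9%. All treated: 0.07506/0.02688 = 2.792, power 79.7%.
- 1%/3%, with exclusion: power 86.9%. All treated: 0.08958/0.02686 = 3.335, power 91.5%.
- 1%/1%: 87.2% with exclusion, 87.0% in all treated.

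**Step 4: how many participants could change a conclusion.** Pooled two-proportion test, 630 per arm in the EAS, with omitted zavegepant participants added as failures and none omitted on placebo.

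- Just-significant MBS result, 236 vs 202 responders: p = 0.044. Adding 3 gives p = 0.051.
- Just-significant pain result, 122 vs 95: p = 0.044. Adding 5 gives p = 0.051.
- At the full planned effect it would take 56 (MBS, 255 vs 202) or 136 (pain, 146 vs 95).

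**The case against.** **The excluded group is narrow.** The criterion is joined by an *or*: one value on any of five measures at any postdose time keeps a participant in. Someone who misses only the 2-hour entry stays and is a failure. This stands, and it is why the number affected is probably small. The nearest figure in the documents is indirect: in the earlier dose-ranging study, 1578 of 1588 treated participants completed (Protocol 4.3), so 10/1588 = 0.6% did not. Completing a study is not completing a diary, so this suggests scale only.

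**A reader might infer that the plan bypasses its own missing-equals-failure rule.** The documents do not support that. Protocol 9.3.2.1 and SAP 6.1 state the rule for analyses on the EAS, and within that set it works as written. The gap lies between the estimand population and the analysis set.

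**A reader might infer that the EAS inflates the effect.** Nothing shows that no-entry rates differ by arm, or which way. The study is double-blind, SAP 4 has set membership settled before unblinding, and Protocol 6.9.2 asks participants to continue handheld entries through 48 hours in all circumstances. Spray discomfort or a severe attack would have to suppress every entry. These are possible mechanisms, not documented ones. Blinded classification does not, however, stop an arm-related cause of silence from affecting who is classified.

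**A reader might set 79.7% against the protocol's 87.5% for MBS.** Those bases differ: 87.5% is for 630 evaluable per arm, 79.7% for 630 treated under one assumed imbalance. The matching figure with exclusion is 86.9%, and the reverse imbalance raises power to 91.5%.

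**The sponsor already reports some counts.** SAP 6.5.3 tabulates analysis sets and SAP 6.5.4 tabulates exposure by arm. Neither asks for the reasons why treated participants left the EAS, and neither analyses them.

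**Conclusion.** The mismatch is real and present in both documents: the estimand covers all who treated a qualifying attack, while the main analysis and both sensitivity analyses cover only those with at least one postdose value. Known early rescue users can be among those removed, and no planned efficacy analysis brings them back.

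Its size cannot be fixed from the documents. Under equal loss it hardly matters: 0.08 points on each endpoint at 1%, and about 0.4 points at 5%. Under unequal loss of 3% and 1%, the EAS overstates the differences by about 0.5 (pain) and 0.9 (MBS) points if the excess is on zavegepant, and understates them by about 0.2 and 0.6 if it is on placebo. These figures assume 630 treated per arm, planned rates holding in the EAS, and no stratification. At the full planned effect a handful of exclusions would not alter the conclusion; in a borderline result a few could. The change is worth making because it aligns analysis with estimand at little cost, not because bias has been shown.

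**What to change.** Delete the postdose-data criterion from the EAS in SAP 4 and Protocol 9.2. No new rule is needed. In the main analysis these participants are failures under NC=F or RM=F. In the sensitivity analyses they are missing at 2 hours, unless rescue by 2 hours already makes them failures. The covariates listed in SAP 5.3 for the pain-freedom imputation are all baseline or predose, so having no postdose entries does not prevent imputation. Keep the current EAS as a supplementary table.

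Record the change in SAP 2.1. The opening of Protocol 9 asks for an amendment where a modification of the primary analyses is major, so the sponsor should decide and document whether this one is.

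At minimum, leave the EAS as it is but prespecify a sensitivity analysis of both co-primaries in all randomized participants who took study intervention with moderate or severe pain, counting no postdose data as failure. Report the number excluded by arm, with reasons.

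Cost: one deleted bullet and a changed flag, or one added table, plus a short amendment if required. Response rates become marginally lower.
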